C.2. Study Overview. *Suubi4Stigma*, a mixed-methods sequential explanatory study,⁹³ will address the urgent need for theoretically and empirically informed interventions that seek to reduce HIV/AIDS-associated stigma and its negative impact on child health and psychosocial well-being. We will test the feasibility, acceptability and preliminary effects of the G-CBT versus MFG intervention, two evidence-based interventions that have, to date, been extensively used to address mental health functioning among children and adolescents. Specifically, clinics will be randomized to one of three study arms (see C.3). The conceptual model (Fig 1) specifies the expected relationship between the intervention arms, mechanisms and potential outcomes.

Figure 2. *Suubi4Stigma* Assessment

usual (n=3 clinics; 30 child-caregiver dyads); 2) G-CBT intervention + usual care (n=3 clinics; 30 child-caregiver dyads); and 3) MFG intervention + usual care (n=3 clinics; 30 child-caregiver dyads). Both treatment and control arms will be delivered over a 3-month period. Data will be collected at baseline (pre-intervention), 3-months and 6-months post-intervention initiation. Children in the same clinic will be assigned to the same study condition to avoid contamination (Fig.2).

C.3.1 Study Inclusion/Exclusion Criteria: *Inclusion criteria for children:* The target population for this study is CLWH enrolled in care at a health clinic that has partnered with ICHAD ([name] et al.; *Suubi+Adherence* study). Child inclusion criteria are: 1) HIV+ status- defined as a child tested with confirmation by medical report and has been disclosed to; 2) prescribed ART; 3) living within a family (defined broadly - not necessarily with biological parents); and 4) ages 10 to 14. All eligible CLWH from a particular household will be enrolled in the study and will be assigned to the same study condition. *Inclusion criteria for parents/caregiving families.* Caregivers of CLWH who agree to participate in the study. *Exclusion criteria* includes a significant cognitive impairment of the child or parent that interferes with understanding the informed consent process. *Inclusion criteria for clinics.* Clinics registered and supported by the government to provide ART to CLWH in Masaka.

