C.3.2. Research Setting: The child-caregiver dyads will be selected from 9 health clinics in the Masaka region where Reach the Youth-Uganda (RTY), our collaborating institution, collaborates with over 40 health clinics (see letters of support). Nine clinics will be randomly selected based on size (total number of CLWH served) and location (rural, semi-urban, urban).

C.3.3. Recruitment of Participants: *Screening and Recruitment.* Procedures tested in our previous studies (see C.1.) will be used. Participants will be identified and recruited from the healthcare clinics associated with RTY and ICHAD. A list of all eligible families will be created from medical records. Providers will present the project to adult caregivers of eligible children during appointments. If caregivers are interested, verbal consent to be contacted by research staff (on-site during clinics) will be requested (see human subjects sections).

Informed Consent. During the face-to-face meeting, the child's primary caregiver will read and sign a standard consent form. In doing so, the caregiver will be consenting to participation for themselves and their child. Children will sign an assent form that will be read aloud verbatim. If either the child or the caregiver refuses to participate, they will not be enrolled. (see human subjects section). *Enrollment.* Dyads will be enrolled in one of the three study arms. Only children and their caregivers who meet inclusion criteria will be selected (See C.3.1.). For each of the 9 clinics, a list of "eligible participants" will be generated and used to randomly select 10 children (and their caregivers), constituting the "actual" participants for that clinic. For the qualitative component, dyads with the highest, medium, and lowest levels of attendance in two treatment arms (6 clinics) will be identified post intervention. Two families within each of these groups in the 6 treatment clinics will be invited to participate in qualitative interviews (2x3x6=36 dyads). This sampling method will ensure that participants with varying experiences are represented. This will allow us to identify common patterns and

variations in participants' experiences. The sample size will be sufficient for theoretical saturation,⁹³⁻⁹⁶ and will allow for identification of common patterns and/or variations across participant experiences.

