Gender, family composition/structure, income, caregiver education & employment	Socio-demographic questionnaire <small>13-42, 100-137, 1-8</small>	n/a	B, 3, 6
Moderators			
Rural/urban/semi-urban: economic/household income, gender		n/a	B, 3, 6
Mechanisms of Change			
Shared experiences, peer and family support, family communication, interpersonal and coping skills	Semi-structured interviews	n/a	6
(Respondent: Adolescent)			
Mental Health Functioning	Youth Self-Report ¹³ Adapted Child Depression Inventory ¹⁵ Adapted Tennessee Self-Concept Scale (TSC-2) ¹ (tested in Suubi Studies)	n/a 0.65 0.81	B, 3, 6
Post-Traumatic Stress Disorder	Beck Hopelessness Scale ¹⁹ The Child PTSD Reaction Index ⁴⁰	0.79 0.88	B, 3, 6
Family Support	Social Support Behaviors Scale (SS-B) ⁴¹	0.77	B, 3, 6
Social Support	Friendship Qualities Scale ^{42,43}	0.81-0.88	B, 3, 6
Stigma and Shame	The Shame Questionnaire ^{44,45} Stigma-by-association scale for children ⁴⁶ HIV Stigma mechanism measure ⁴⁷	0.84- 0.89-0.90 0.87-0.89	B, 3, 6
Medication Adherence	Youth Self Report, ⁴⁸ Viral loads Pill Counting, Pharmacy Records	n/a n/a	B, 3, 6 Ongoing
Loneliness and Social Isolation	UCLA Loneliness Scale Version 3 ⁴⁹ The Lubben Social Network Scale (LSNS-18) ⁵⁰	0.89-0.94	B, 3, 6
Sexual risk taking	Adapted Youth AIDS Prevention Project used in CHAMP ⁵¹⁻⁵² Questions adapted from Auslander et al. ⁵³ & Stolni-Ngovo et al. ⁵²	n/a 0.72	
Intervention feedback	Semi-structured interviews	n/a	6
(Respondent: Caregiver)			
Stigma and Shame	AIDS-related stigma scale ⁵³ HIV/AIDS Stigma and Discrimination ⁵⁴	0.75 0.72-0.85	B, 3, 6
Family Relations	Family Environment Scale/Family Assessment Measure ^{55-56,58}	0.54-0.87	B, 3, 6
Intervention feedback	Semi-structured interviews	n/a	6
COST			
Cost of staff time, supplies, overhead for mental health and economic interventions	Project records, Admin. review	n/a	ongoing

conducted for all measures to ensure cultural validity. Process measures will be used to monitor fidelity and intervention implementation.

Intervention Delivery Fidelity. Independent observations using rating scales will be made with a random sample of 60% of intervention sessions for both G-CBT and MFG. These data will be used to assess: 1) the relationship between planned and actual implementation; 2) the integrity of implementation and; 3) how were altered to maximize effectiveness and acceptability.

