b) *Acceptability.* We will adapt satisfaction surveys, (e.g., the Client Satisfaction Questionnaire (CSQ-8)) to assess acceptability.¹⁶⁰ Items include: "How satisfied were you with the program?", "How helpful was the program in addressing HIV-associated stigma?" and "How likely are you to recommend this program to other families with CLHA?" Given the modest sample size, quantitative analyses of intervention data will be largely descriptive and concentrate on tabulating and summarizing satisfaction outcomes. In regards to hypotheses and methods for primary preliminary/exploratory analyses *to assess study feasibility*, we expect that: **H1:** Following intervention, relative to the control group, participants in both treatment arms (G-CBT and MFG) will have: **H1a:** lower mean count of children reporting HIV/AIDS-associated stigma; **H1b:** lower mean levels of reported HIV/AIDS-associated stigma and improved child psychosocial functioning; **H1c:** lower mean levels of reported child mental health challenges; **H1d:** higher mean levels of adherence. **H2:** Following intervention, relative to the CBT intervention arm, participants in the MFG intervention will have: **H2a:** lower mean count of children reporting HIV/AIDS-associated stigma; **H2b:** lower mean levels of reported HIV/AIDS-associated stigma and improved child psychosocial functioning; **H2c:** lower mean levels of reported child mental health challenges; **H2d:** higher mean levels of adherence. Children will be the unit of analysis for these primary preliminary analyses. We will plot means by group over time to describe overall patterns of change. We will use linear mixed models (LMMs) to evaluate the proposed hypotheses. We will fit LMMs to ensure that all requisite information is available to perform the types of analyses typically undertaken in a formal RCT of intervention efficacy and to obtain valuable effect size information. LMMs will include random intercepts for clinic membership and random intercepts and slopes for subjects (three-level models). Due to the modest sample size, significance testing will be de-emphasized. Similarly, although the modest sample size precludes formal investigation of moderation, we will use the same LMM approach described above to compare children across study arms over time on the moderators listed in Table 1. Additional analyses will consider the role of child gender as a moderator in line with NIH guidelines addressing the importance of sex and gender as critical moderators. These moderation analyses will be secondary exploratory analyses. Additional exploratory analyses will study parents and children jointly as the unit of analysis via dyadic analysis methods such as actor-partner and means-and-deviation models to quantify parent vs. child stigma effects and between- vs. within-dyad effects on mental health outcomes.^{161,162}

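### The draw of ten children per clinic does not use sex, although gender moderation is planned; stratifying the draw and adjusting for sex would give a modest gain at almost no cost

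*Combined protocol and SAP*

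**What the plan says.** All references are to the Combined protocol and SAP.

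- **Selection of children (C.3.3).** The list of eligible families is built from medical records. For each of the nine clinics a list of eligible participants "will be generated and used to randomly select 10 children (and their caregivers"). No sex stratum or quota is stated here or elsewhere.
- **Selection of clinics (C.3.2).** "Nine clinics will be randomly selected based on size (total number of CLWH served) and location (rural, semi-urban, urban"). Sex plays no part.
- **Allocation (C.2 and the arm description after it).** "clinics will be randomized to one of three study arms", and each arm is small, for example "MFG intervention + usual care (n=3 clinics; 30 child-caregiver dyads").
- **Household rule (C.3.1).** "All eligible CLWH from a particular household will be enrolled in the study and will be assigned to the same study condition".
- **Moderators (Table 1).** "Rural/urban/semi-urban: economic/household income, gender".
- **Analysis (C.3.6 Data Analysis, Aim 1).** The plan will examine "the role of child gender as a moderator in line with NIH guidelines addressing the importance of sex and gender as critical moderators". The same paragraph says that the sample size rules out a formal study of moderation, and it labels these analyses secondary and exploratory. The mixed model is described only by its random effects: a clinic intercept, and an intercept and slope for each child.

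**The concern.** The plan names gender as a variable of interest and should know it before the draw, but does not use it. With ten children per clinic and three clinics per arm, chance alone can give a clinic very few boys or very few girls, and neither clinic selection nor clinic randomisation corrects for this.

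Two things are at stake. A clinic with a lopsided draw adds little to the comparison of boys with girls, so the gender analysis loses precision. And if an outcome differs by sex, a chance difference in sex mix between arms enters the plotted means and any arm contrast that is not adjusted for sex. The plan plays down significance testing and presents effect sizes as a main product, so the estimates themselves deserve protection.

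**Working it through.** **Inputs from the documents.** 10 children per clinic, 3 clinics and 30 children per arm, 9 clinics; 81 of 90 retained (27 per arm, 9 per clinic); clinic ICC 0.093; alpha 0.05; power 0.80; stated detectable difference 0.79 to 0.97 SD for within-subject correlation r from 0.20 to 0.80.

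**Assumptions, not in the documents.** Half of eligible children are girls (40% or 60% as a variant); list lengths of 20, 40 or very long; a sex difference in the outcome of 0.3 to 0.5 SD.

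**1. The plan's own figure.** The documents give no figure for sex balance, so the detectable difference serves as the yardstick. Design effect = 1 + (9 − 1) × 0.093 = 1.744. Standard error = √(2/27) × √(1.744 × (1 + r)/2), which is 0.278 at r = 0.20 and 0.341 at r = 0.80. Multiplying by 1.960 + 0.842 gives 0.780 and 0.955. The noncentral t version with 52 degrees of freedom gives 0.795 and 0.973, which agrees with the stated figures.

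**2. Imbalance within clinics.** For a very long list the number of girls is Binomial(10, 0.5). P(2 or fewer of one sex) = 2 × (1 + 10 + 45)/1024 = 0.109. For at least one of nine clinics, 1 − (1 − 0.109)^9 = 0.647. For shorter lists that are half girls, the hypergeometric distribution applies.

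| List | Per clinic | At least one of nine |
|---|---|---|
| 20 | 2.3% | 19% |
| 40 | 6.5% | 45% |
| Very long | 10.9% | 65% |
| Very long, 40% or 60% girls | 18.0% | 83% |

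**3. Imbalance between arms (very long lists, half girls).** The difference in the number of girls between two arms has the distribution of Binomial(60, 0.5) − 30. P(difference of 6 or more, which is 20 points) is about 15% for a given pair (15.5% exactly). For some pair among the three arms it is 33%. With lists of 20, simulation gives about 5% and 12%.

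**4. Information on the within-arm sex contrast.**

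- *Within clinics.* The information per clinic is (boys × girls)/10, in units of 1/within-clinic variance. A 5+5 draw gives 2.50. A random draw from a very long list gives on average (25 − 2.5)/10 = 2.25. Over three clinics this is 6.75 against 7.50, a 10% loss if only within-clinic information counts.
- *Between clinics.* The planned random clinic intercept recovers part of this. The expected sum of squared deviations of the three clinic sex shares is 2 × 0.025 = 0.05. The variance of a clinic mean is 0.093 + 0.907/10 = 0.1837. The between-clinic information is 0.05 × 0.907/0.1837 = 0.25.
- *Total.* 6.75 + 0.25 = 7.00 against 7.50, a loss of about 7%, or about 3.5% in standard error.
- *Shorter lists.* With lists of 20 the variance of the number of girls falls to 2.5 × 10/19 = 1.316. The total is 3 × (25 − 1.316)/10 + 2 × 0.01316 × 0.907/0.1837 = 7.105 + 0.130 = 7.24, a loss of about 4%.

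**5. Shift in an arm contrast.** A 20-point imbalance times a 0.3 to 0.5 SD sex difference gives 0.20 × 0.3 = 0.06 to 0.20 × 0.5 = 0.10 SD. Against the standard errors in step 1 this is between 0.06/0.341 = 0.18 and 0.10/0.278 = 0.36 of a standard error. Against the detectable difference it is between 0.06/0.97 = 6% and 0.10/0.79 = 13%.

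**6. How often five of each sex are available.** If each listed child is a girl with probability 0.5, at least one of nine clinics has fewer than five of one sex with probability 68% for lists of 15 and 10% for lists of 20.

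**The case against.** A random draw of ten is a valid design, and a 5+5 draw is a refinement rather than the repair of an error. The plan already limits moderation to secondary exploratory work. Even with perfect balance the detectable sex-by-arm interaction would be about 1.18 to 1.45 SD, or 1.56 to 1.91 SD with the clinic design effect, so balance does not make the interaction testable. This stands, and it keeps the point modest.

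A sex difference that is stable over time is also present at baseline and largely cancels in an arm-by-time contrast. This stands for that contrast. It is not a complete answer, because the hypotheses speak of mean levels after intervention, and the plan's detectable difference reproduces with the factor (1 + r)/2, which belongs to an average over two time points rather than to a change.

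Some stronger readings go beyond the documents:

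- *The arms will be badly unbalanced.* A 20-point gap has about a 15% chance for a given pair of arms even with very long lists, and its effect is small beside the stated detectable difference. Lopsidedness is mainly a matter of single clinics.
- *A 5+5 draw abolishes the problem.* Balance holds only at the draw and only where five of each sex are eligible. Siblings enrolled under C.3.1, refusals and the assumed 10% attrition can all disturb it.
- *Gender is the trial's one critical moderator.* Table 1 lists it with location and household income, and the word critical comes in the plan's reference to NIH guidelines.
- *The model excludes sex.* The plan lists no fixed effects at all, so the absence of sex shows only that it is not specified.

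**Conclusion.** The point holds as a worthwhile, inexpensive improvement. The draw ignores a variable that should be at hand and that the plan intends to analyse. The chance that at least one clinic has two or fewer of one sex is about 19%, 45% or 65% for lists of 20, 40 or very long lists, if half of eligible children are girls. An unequal mix raises it, to 83% at 40% or 60% girls with very long lists.

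The consequences are modest: on average about 7% of the information on the within-arm sex contrast with very long lists and less with short ones, and at most about 0.06 to 0.10 SD in an unadjusted arm contrast for a 20-point imbalance, much less in an arm-by-time contrast. The documents give neither list lengths nor the sex ratio nor a sex effect, so these figures are ranges under assumption. A reader might infer that the arm comparisons are compromised or that the gender analysis could be made confirmatory. Neither inference is supported.

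**What to change.** 1. In C.3.3, stratify each clinic's random draw by sex where the list allows: aim for five boys and five girls, fill from the other sex where fewer than five are eligible, and record each clinic where this happens.
2. State how the draw works with the C.3.1 household rule. Enrolling every eligible child in a household does not fit a fixed ten per clinic and can also break a 5+5 split, so the two passages need to be reconciled.
3. In C.3.6, list sex as a fixed covariate in the linear mixed models for the main arm contrasts. This deals with most of any remaining shift, including imbalance that arises after the draw.

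The cost is a sentence or two in the selection procedure and one model term, for a variable that is already collected. The downside is that where a clinic's eligible children are not half girls, the sample no longer mirrors that ratio. The draw should be changed before enrolment, since it cannot be repeated afterwards.

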Implementation/Evaluation. Having two facilitators per group will allow for detailed process notes on the implementation process and balancing “fidelity” and “fit” to local culture. Changes from the planned curriculum will be examined using process notes. Caregivers/children will report monthly on factors that affect their participation using an implementation checklist that assesses satisfaction and obstacles to program delivery: 1) factors interfering with youth or family participation (e.g. time, other priorities, stigma); 2) concrete obstacles (e.g. weather, transportation); and 3) site and staffing obstacles (e.g. time constraints).

C.3.6. Semi-structured Interviews (Aim 2). These interviews will: 1) Explore participants’ intervention experiences and perceived impact of the intervention on change mechanisms (including shared experiences, peer and family support, family communication, interpersonal and coping skills); and 2) Identify multi-level facilitators and barriers to G-CBT and MFG intervention, implementation and participation. Participants in the two treatment arms will be asked for feedback on intervention acceptability and relevance via semi-structured interviews upon intervention completion. Semi-structured in-depth interviews will be conducted with caregivers and CLWH separately at post intervention for each treatment arm. The interviews will provide rich data on participants’ processes and experiences with the program; processes behind key outcomes, mechanisms of change and mediating variables; and potential individual, family, contextual, programmatic, and structural factors affecting their experiences. At the end of the intervention, all facilitators will also be interviewed to gain a deeper understanding of implementation patterns and processes, including their views on sustainability. Interviews will be conducted in English or Luganda. Questions will be translated/back-translated by two team members fluent in both languages. Interviews will last about 1 hour and will be audio-taped.

C.3.6. Data Analysis

Aim 1: Feasibility and Acceptability. a) **Feasibility.** We will monitor recruitment rates and staff level of effort, number of screenings conducted, proportion eligible and agreed to enroll. Enrollment of 70% or higher will be

considered feasible.¹⁵⁹ We will also record the number of rescheduled, cancelled and missed sessions and assessments to inform estimation of staffing needs and retention protocols for a subsequent trial.

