C.4. Study Timeline (Over 24 months): Study preparations, adaptation/refinement of interventions and instruments (months 1-3); Participant recruitment and baseline assessments (months 4-6); Intervention delivery (months 7-9); Post intervention assessments and follow-up (months 10-15); Data entry, analysis, report writing and dissemination of findings (months 4-24) (see study timeline).

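### Interview timing differs between C.3.6 (end of intervention) and Table 1 (month 6); on the C.3.6 timing, up to 60% of treated dyads and no controls are interviewed before the month-6 outcomes

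*Combined protocol and SAP*

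**What the plan says.** The timing of the interviews is given in two ways.

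- **Section C.3.6, Semi-structured Interviews (Aim 2).** Participants in the two treatment arms give feedback "via semi-structured interviews upon intervention completion". The section adds: "Semi-structured in-depth interviews will be conducted with caregivers and CLWH separately at post intervention for each treatment arm". Each interview lasts about an hour.
- **Table 1.** The mechanisms-of-change row reads "interpersonal and coping skills Semi-structured interviews n/a 6". The adolescent and caregiver feedback rows also give time point 6 alone. Most of the questionnaire rows in the same table are marked for baseline, 3 and 6.

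The surrounding design fixes what these mean in months. The design paragraph beside Figure 2 says "Both treatment and control arms will be delivered over a 3-month period" and "Data will be collected at baseline (pre-intervention), 3-months and 6-months post-intervention initiation". Section C.3.3 draws the interviewed families from the six treatment clinics only, two from each of three attendance levels per clinic ("2x3x6=36 dyads"). Section C.4 gives "Intervention delivery (months 7-9); Post intervention assessments and follow-up (months 10-15") but does not date the interviews.

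**The concern.** If the interviews take place when delivery ends, they fall between the month-3 and month-6 assessments, and only in the treated arms. Their topics include "Shared experiences, peer and family support, family communication, interpersonal and coping skills". These overlap with what the interventions work on: coping skills in G-CBT, communication and support in MFG. The children and caregivers interviewed then complete month-6 self-report scales on stigma, family relations or support and, for children, mental health.

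An in-depth conversation on these themes could change how people answer, and no control dyad would have one. The comparison exposed to this is each active arm against control at month 6 (H1). Significance testing is de-emphasised in the Aim 1 analysis, but effect sizes from the mixed models are a stated product of the study, so an avoidable difference between arms before the last measurement deserves attention.

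**Working it through.** **1. Where the interviews fall.** Delivery takes 3 months and the last assessment is 6 months after initiation. Interviews at completion therefore come about 6 − 3 = 3 months before the final outcomes. Under Table 1 they fall at the month-6 time point itself, and the order within that visit is not stated.

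**2. The plan's own count.** 2 families × 3 attendance levels × 6 clinics = 36 dyads, which reproduces the figure in C.3.3. With child and caregiver seen separately, that is 36 × 2 = 72 interviews.

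**3. Share exposed before month 6 on the C.3.6 timing.**

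| Group | Interviewed | Enrolled | Share |
|---|---|---|---|
| G-CBT | 18 | 30 | 60% |
| MFG | 18 | 30 | 60% |
| Both treated arms | 36 | 60 | 60% |
| Control | 0 | 30 | 0% |

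Each treatment clinic contributes 2 × 3 = 6 of its 10 dyads. These shares assume that every invited dyad accepts. Among those retained, the power section's 10% attrition gives 90 × 0.90 = 81, or 27 per arm and 54 treated. If all 36 interviewed dyads stay in, the share is 36/54 = 67%.

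**4. What a shift would do (assumption, not from the documents).** The documents give no effect of an interview on the outcomes. Suppose it moves the interviewed children by *s* standard deviations, in either direction, and take *s* from 0.1 to 0.5 for illustration.

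- Active arm against control: 0.60 × *s*, so 0.60 × 0.1 = 0.06 SD to 0.60 × 0.5 = 0.30 SD.
- Against the stated minimum detectable differences of .79 to .97: 0.06/0.97 = 6% at the low end, 0.30/0.79 = 38% at the high end.
- MFG against G-CBT: 0.60 × *s* − 0.60 × *s* = 0, provided that uptake and *s* are the same in both arms.

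**5. With interviews after the month-6 questionnaires.** The share exposed before the outcome is 0% in every arm.

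**The case against.** The best defence is that the conflict is one of loose wording. Section C.3.6 names no month. Section C.4 applies the post-intervention label to a span of study months 10 to 15, which can include the month-6 visit. Table 1 holds the only numeric timing and gives 6 in all three interview rows. The study calls itself sequential explanatory, and the integration plan uses qualitative findings to explain quantitative ones. Both fit interviews held after the outcome data.

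This makes month 6 a reasonable reading, but it does not settle the matter. The phrase about completion most naturally points to the end of delivery, and even on the month-6 reading the order of interview and questionnaires is open.

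Other parts of the defence stand and limit the point:

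- A reader might take the interview to be an hour about stigma. The topic list does not name stigma; it reaches it only through a general reference to the key outcomes. The interviews also cover barriers, acceptability and relevance.
- A reader might count the interview as one more hour on top of ten one-hour sessions. Nothing in the documents supports treating a research interview about the programme as equal to a session that delivers it.
- H1 already compares added group sessions with usual care alone, so contact differs by design. The study's purpose is feasibility and acceptability.
- Viral load, pill counts and pharmacy records are not self-report, so the concern about questionnaire answers does not carry over to them.
- Later interviews mean longer recall for children aged 10 to 14.

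**Conclusion.** The two timings conflict and should be reconciled. On the C.3.6 timing, up to 36 of 60 treated dyads and 0 of 30 controls are interviewed about three months before the final outcomes. The 60% rests on full acceptance; lower uptake reduces it in proportion.

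This is unequal exposure that could shift the month-6 effect sizes for H1. A reader might infer that H1 is biased, or biased in favour of treatment. The documents do not support that: they give no size and no direction for an interview effect, and the 0.06 to 0.30 SD above follows entirely from an assumed range. Nor does the point extend to H2, where the planned share is 18 of 30 in each arm. Month 3 would be touched only if interviews came before that visit's questionnaires, which the plan does not say. Severity is minor.

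**What to change.** State in both C.3.6 and Table 1 that each dyad's child and caregiver interviews take place after that dyad has completed its month-6 quantitative assessment. This agrees with the table and with the sequential explanatory design. Dyads can still be selected by attendance once the intervention ends, as C.3.3 provides. The member-check focus groups in the Aim 2 analysis carry no date; any that include participants should follow the same order.

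The cost is a change of wording and about three months' longer recall of the sessions. Table 1's timing already implies that recall.
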